## 6.9 Safety Monitoring and Procedures

### 6.9.1 Adverse Events

Subjects will be instructed to inform the study physician and/or research personnel of any AEs that occur at any time during the study. Subjects will be monitored for AEs from the first dose through the end-of-study visit.

Refer to Section 7 for details regarding AE reporting.

### 6.9.2 Clinical Laboratory Evaluations

Clinical laboratory evaluations will be performed at the times noted on the events schedule (Table 6 for food-effect cohorts and Table 7 for non-food-effect cohort). A Clinical Laboratory Improvement Amendments (CLIA) certified laboratory will perform all clinical laboratory tests for this study. If exclusionary lab criteria are met, values may be confirmed by repeat evaluation.

- Hematology: hemoglobin, hematocrit, total and differential leukocyte count, red blood cell count (RBC), and platelet count.
- Serum Chemistry: albumin, blood urea nitrogen (BUN), creatinine, total bilirubin, alkaline phosphatase (ALP), aspartate transaminase (AST), alanine transaminase (ALT), sodium (Na+), potassium (K+), chloride (Cl), lactate dehydrogenase (LDH), calcium (Ca), uric acid, glucose, gamma-glutamyltransferase (GGT), and magnesium.
- Serology: hepatitis B surface antigen, hepatitis C antibody, and HIV.
- Coagulation: prothrombin time (PT), partial thromboplastin time (PTT), and international normalized ratio (INR).
- Urinalysis - The following will be evaluated by an automated or manual urine “dipstick” method: pH, specific gravity, protein, glucose, ketones, bilirubin, blood, nitrite, leukocyte esterase, and urobilinogen. If protein, occult blood, nitrite, or leukocyte esterase values are out of range, a microscopic examination will be performed.
- Urine Drug, Cotinine, and Alcohol Screens: drugs of abuse (amphetamines, benzodiazepines, barbiturates, cannabinoids, cocaine, opiates), alcohol, and cotinine.
- Pregnancy test (all female subjects).
- Follicle-stimulating hormone (female subjects claiming post-menopausal status).

#### 6.9.3 Vital Signs

Vital signs (blood pressure, pulse rate, and respiration rate, pulse oximetry, and temperature) will be measured performed at the times noted on the events schedule ([Table 6](#) for food-effect cohorts and [Table 7](#) for non-food-effect cohort).

NOTE: Blood pressure and pulse rate will be captured simultaneously. Blood pressure and pulse rate should be measured after subjects are in a seated position for 2 minutes and then again after standing for 1 minute, except when they are supine or semi-reclined because of study procedures and/or adverse events, or as deemed necessary by the Investigator.

For purposes of qualifying any given subject for study participation, out-of-range vital signs may be repeated once.

Predose vital signs will be assessed by the Principal Investigator or designee (e.g., a medically qualified Sub-Investigator) prior to each study drug administration. The Principal Investigator or designee will verify the eligibility of each subject with out-of-range vital signs and document approval prior to dosing.

Additional vital signs measurements may be performed as deemed medically necessary by research personnel.

#### 6.9.4 Physical Examinations

Physical examinations, including height and weight measurements, will be conducted at the times noted on the events schedule ([Table 6](#) for food-effect cohorts and [Table 7](#) for non-food-effect cohort).

#### 6.9.5 Neurological Examinations

Detailed neurological examinations will be conducted at the times noted on the events schedule ([Table 6](#) for food-effect cohorts and [Table 7](#) for non-food-effect cohort) and at unscheduled time points as deemed necessary by the Investigator. Each neurological exam will assess the following:

- Mental Status – orientation, speech, and memory
- Cranial Nerves – excluding fundoscopic examination
- Muscle tone and strength
- Sensory System – brief survey for light touch and temperature of the face, neck, arms, trunk, and legs
- Reflexes –deep tendon reflexes and plantar responses (Babinski sign)
- Coordination – upper and lower extremities, including tremor
- Gait – tandem gait

#### 6.9.6 12-Lead Electrocardiograms

Safety 12-lead ECGs will be recorded and printed for on-site review by the Principal Investigator or designee at the times noted on the events schedule ([Table 6](#) for food-effect cohorts and [Table 7](#) for non-food-effect cohort).

The predose ECG should be completed within 20 minutes prior to the predose blood draw.

All safety ECGs will be performed after the subject has been in supine position for a minimum of 5 minutes.

If a subject experiences a post-dosing QTcF  $>500$  msec or a change-from-baseline QTcF  $\geq 60$  msec, after repeat testing, additional ECGs should be recorded until normalization or return to baseline.

#### 6.9.7 Other Safety Measures

Medical emergency personnel trained in advanced cardiac life support will be on site to monitor subjects during the confinement period in the research center. Emergency

medical equipment including but not limited to intubation equipment and pulse oximetry shall be maintained on site to administer appropriate medical care should it be required.

Procedures will be completed as specified in this protocol unless contraindicated due to a reported AE.

## 7 ADVERSE EVENTS

The Investigator or a suitably medically qualified designee are responsible for eliciting adverse events by observing and questioning the subject and recording all adverse events observed by him/her or reported by the subject during the trial.

### 7.1 Definitions

#### 7.1.1 Adverse Event

Any untoward medical occurrence in a clinical investigation participant, temporally associated with the use of a trial treatment whether or not considered related to trial treatment. An adverse event can therefore be any unfavorable and unintended sign (including an abnormal laboratory finding), symptom, or disease (new or exacerbated) temporally associated with the use of a trial treatment, whether or not related to the trial treatment.

#### 7.1.2 Serious Adverse Event

Any untoward medical occurrence that at any dose:

- Results in death;
- Is life threatening (any event in which the participant was at risk of death at the time of the event; it does not refer to an event, which hypothetically might have caused death if it were more severe);
- Requires inpatient hospitalization or prolongation of existing hospitalization; In general, hospitalization signifies that the participant has been detained (usually involving at least an overnight stay) at the hospital or emergency ward for observation and/or treatment that would not have been appropriate in the physician's office or outpatient setting. Complications that occur during hospitalization are AEs. If a complication prolongs hospitalization or fulfills any other serious criteria, the event is serious. When in doubt as to whether "hospitalization" occurred or was necessary, the AE should be considered serious. Hospitalization for elective treatment of a pre-existing condition that did not worsen from baseline is not considered an AE;
- Results in persistent or significant disability/incapacity; the term disability means a substantial disruption of a person's ability to conduct normal life functions. This

definition is not intended to include experiences of relatively minor medical significance such as uncomplicated headache, nausea, vomiting, diarrhea, influenza, and accidental trauma (e.g., sprained ankle) which may interfere with or prevent everyday life functions but do not constitute a substantial disruption;

- Is a congenital anomaly/birth defect; or
- Is a medically important event.

Note: Medical and scientific judgment should be exercised in deciding which is a medically important event that may not be immediately life-threatening or result in death or hospitalization, but may jeopardize the participant or may require medical or surgical intervention to prevent one of the outcomes listed above. Examples of such events are intensive treatment in an emergency room or at home for allergic bronchospasm, blood dyscrasias or convulsions that do not result in hospitalization, or the development of drug dependency or drug abuse. A “suspected transmission of infectious agent by a medicinal product” is also considered a serious adverse event under the SAE criterion “Other medically important condition”.

## 7.2 Attribution/Causality

An adverse reaction, the nature or severity of which is not consistent with the applicable product information (e.g., Investigator's Brochure for an unapproved investigational product).

- The investigator is obligated to assess the relationship between trial treatment and each occurrence of each AE/SAE.
- The investigator will use clinical judgment to determine the relationship.
- Alternative causes, such as underlying disease(s), concomitant therapy, and other risk factors, as well as the temporal relationship of the event to trial treatment administration will be considered and investigated.
- The investigator will also consult the Investigator's Brochure and/or Product Information, for marketed products, in his/her assessment.
- For each AE/SAE, the investigator must document in the medical notes that he/she has reviewed the AE/SAE and has provided an assessment of causality.
- There may be situations in which an SAE has occurred and the investigator has minimal information to include in the initial report to the Sponsor/designee. However, it is very important that the investigator always make an assessment of causality for every event before the initial transmission of the SAE data to the Sponsor/designee.

- The investigator may change his/her opinion of causality in light of follow-up information and send a SAE follow-up report with the updated causality assessment.

**Table 10 Adverse Event Attribution/Causality Ratings**

Relatedness Rating	Definition
Not Related	An adverse event, which is not related to the use of the drug.
Unlikely	An adverse event for which an alternative explanation is more likely, e.g., concomitant drug(s) or concomitant disease(s), and/or the relationship in time suggests that a causal relationship is unlikely.
Possible	An adverse event, which might be due to the use of the drug. An alternative explanation, e.g., concomitant drug(s) or concomitant disease(s), is inconclusive. The relationship in time is reasonable; therefore, the causal relationship cannot be excluded.
Probable	An adverse event, which might be due to the use of the drug. The relationship in time is suggestive, e.g., confirmed by dechallenge. An alternative explanation is less likely, e.g., concomitant drug(s) or concomitant disease(s).
Certain	An adverse event, which is listed as a possible adverse reaction and cannot be reasonably explained by an alternative explanation, e.g., concomitant drug(s) or concomitant disease(s).

**Table 11 Definitions for Adverse Event Severity Gradings**

Grade	Severity Rating	Definition
GRADE 1	Mild	Transient or mild discomfort (< 48 hours); no medical intervention/therapy required.
GRADE 2	Moderate	Mild to moderate limitation in activity - some assistance may be needed; no or minimal medical intervention/therapy required.
GRADE 3	Severe	Marked limitation in activity, some assistance usually required; medical intervention/therapy required, hospitalizations possible.
GRADE 4	Potentially Life-Threatening	Extreme limitation in activity, significant assistance required; significant medical intervention/therapy required, hospitalization or hospice care probable.

See Appendix 3 for full DMID Toxicity Tables. The above ratings should be used to estimate the grade for abnormalities NOT found elsewhere in the Toxicity Tables. Lab results within the testing facility's normal range will not be considered AEs when referenced to the DMID assessment/grading scale (Appendix 3).

Laboratory abnormalities and cardiovascular findings of hypertension or hypotension Grade 2 or above on the DMID toxicity tables will be considered AEs.

### **7.3 Reporting**

#### **7.3.1 Adverse Event**

Adverse Events will be collected by the Investigator or qualified designee(s) from the time a subject signs the Informed Consent Form through the follow-up phone calls (Day 14 for the Single Ascending Dose Cohort and Day 28 for the Multiple Ascending Dose Cohorts).

Any AE (serious or non-serious) observed by the Investigator (or a suitably medically qualified designee) or reported by the subject will be recorded on the Adverse Event Case Report Form. The Investigator will review each AE and assess its relationship to drug treatment based on all available information at the time of the completion of the CRF. The following information will be recorded for each Adverse Event reported:

- Diagnosis of the AE, if possible. In the case where an overall diagnosis cannot be made, each specific sign and/or symptom will be recorded as individual AEs;
- Date of onset;
- Stop date (with duration, if applicable);
- Severity;
- Action taken with IMP;
- Other action taken;
- Outcome;
- Relationship to IMP;
- Occurrence;
- Seriousness

### **7.4 Serious Adverse Event Reporting**

The Investigator or designee will notify the appropriate Sponsor contact immediately after the SAE detection, observation, or report of occurrence (regardless of the relationship to test article). The Sponsor contact information for SAE reporting is provided below:

TB Alliance Pharmacovigilance  
Email: [[name]](mailto:[name])

Questions relative to SAE processing may also be sent to the above mentioned email address. If there is ever any email failure upon trying to report an SAE, please call [name] at [contact] and he will notify the safety team at TB Alliance.

Medical questions relative to AEs and SAEs can be directed to:

[name]  
Global Alliance for TB Drug Development  
[name]  
[name]  
[contact]  
[contact]  
[contact]  
Email: [contact]

These SAE reports must contain the following information:

- A. Study name/number (for EU also the EudraCT number)
- B. Study drug
- C. Investigator details (name, phone, fax, e-mail)
- D. Subject number
- E. Subject demographics
- F. Clinical event:
  - 1) Description
  - 2) Date of onset
  - 3) Treatment (drug, dose, dosage form)
  - 4) Adverse event relationship to study drug
  - 5) Action taken regarding study drug in direct relationship to the AE
- G. If the AE was fatal or life-threatening
- H. If applicable, cause of death (whether or not the death was related to study drug)
- I. If applicable, autopsy findings (if available)

Any new SAE that occurs within one month after the study period and is considered to be possibly related to the Investigational Product (IP) should be recorded and reported immediately to the Sponsor.

The person responsible for the study shall take care that the study has been carried out in accordance with pharmacovigilance local regulations.

All serious event reporting will adhere to U.S. Code of Federal Regulations (21 CFR Part 312.32) for IND drugs and 21 CFR 314.80 for marketed drugs (15-day alerts). The Institutional Review Board (IRB) will be notified of the alert reports per Food and Drug Administration (FDA) regulations.

All AEs, including SAEs, will be followed to resolution when possible. All AEs and treatment administered will be recorded on the case report form (CRF).

The Sponsor will be responsible for processing and reporting any SAEs (and their relevant updates) to the FDA or other applicable regulatory agency.

### **7.5 Follow up of Adverse Events**

All AEs will be followed until:

- Satisfactory clinical resolution or stabilization; or
- End of the follow-up period; and
- All queries on these AEs have been resolved.

Certain long-term AEs cannot be followed until resolution within the setting of this protocol. In these cases, follow-up will be the responsibility of the treating physician. However, this will have to be agreed upon with the Sponsor Medical Monitor.

The investigator is obligated to perform or arrange for the conduct of supplemental measurements and/or evaluations as medically indicated or as requested by Sponsor or representative to elucidate the nature and/or causality of the AE or SAE as fully as possible. This may include additional laboratory tests or investigations, histopathological examinations, or consultation with other health care professionals. Investigator should contact sponsor/designee to discuss appropriate medical follow-up if consultation required.

If a participant dies during participation in the trial or during a recognized follow-up period, the investigator will provide sponsor/representative with a copy of any post-mortem findings including histopathology.

New or updated information on an SAE will be recorded in the originally completed CRF and submitted to sponsor within 24 hours of the information becoming known per SAE reporting guidelines.

### **7.6 Post-Trial Serious Adverse Events**

Any new SAEs reported by the subject to the Investigator that occur up to 30 days after last contact, and are determined by the Principal Investigator to be possible, probable or very likely related to the use of the IMP, will be reported to the Sponsor, IRB and FDA on an expedited basis as required in accordance with local requirements and ICH guidelines for GCP.

### **7.7 Clinical Laboratory Adverse Events**

Changes in the results of the Clinical Laboratory assessment results which the Investigator feels are clinically significant will be reported as adverse events. It is the Investigators' responsibility to review the results of all laboratory tests as they become available. This review must be documented by the Investigators' dated signature on the laboratory report. For each abnormal laboratory test result, the Investigator needs to

ascertain and document if this is a clinically significant change from baseline for that individual participant. This determination, however, does not necessarily need to be made the first time an abnormal value is observed. The Investigator may repeat the laboratory test or request additional tests to verify the results of the original laboratory tests. If this laboratory value is determined by the Investigator to be a clinically significant change from baseline for that participant, it is considered to be an adverse event.

## **7.8 Drug Interaction**

If the Investigator becomes aware that the subject has experienced a drug interaction which has resulted in an adverse event, it will be recorded as an adverse event.

## **7.9 Pregnancy**

The Investigator will immediately notify the Sponsor of any pregnancy that is discovered during the clinical trial. Pregnancy forms will be completed for all pregnancies reported during the study or in the 30 days after completion of the IMP. In addition, the Investigator will report to the Sponsor follow up information regarding the outcome of the pregnancy, including perinatal and neonatal outcome. Infants should be followed for 6 months.

If pregnancy is suspected while the subject is receiving IMP, the IMP will be withheld immediately until the result of the pregnancy test is known. If pregnancy is confirmed, the IMP will be permanently discontinued in an appropriate manner and the subject withdrawn from the trial. Protocol-required procedures for trial discontinuation and follow up will be performed unless contraindicated by the pregnancy.

If the Investigator becomes aware the female partner of a male subject becomes pregnant during the study or in the 30 days after the completion of IMP, consent will be requested from the female partner for collection of information on her pregnancy history and for information on the current pregnancy and birth.

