**Study design overview:**

This is a partially-blinded, placebo-controlled, randomized multiple ascending dose (MAD) study to be conducted at one study center.

Thirty-six (36) subjects will be enrolled in 3 cohorts with 12 subjects per cohort. Within each cohort, 9 subjects will be assigned to receive active treatment and 3 subjects will receive placebo. Each subject will participate in one dose level.

The first 2 cohorts (food-effect cohorts) will begin dosing of TBI-223 on Day 1 under fasted conditions, followed by a 3 day washout period and then by multiple doses of TBI-223 administered

after a high-calorie, high-fat meal from Day 4 through Day 17 (total of 14 days). The third cohort (non-food-effect cohort) will begin dosing of TBI-223 on Day 1 and continue through Day 14, all doses administered after a high-calorie, high-fat meal.

Each subject will be administered TBI-223 tablets (SR1 or IR or a combination of both formulations) or placebo once daily for 14 days with corresponding pharmacokinetic measurements. After each dose cohort, the Sponsor and Investigator will review the pharmacokinetic and safety data before proceeding to the next dose level.

Dose escalation to the next cohort (i.e., dose level) or decisions regarding changed or additional cohorts will not take place until the Sponsor, in conjunction with the Principal Investigator and dose escalating committee, has determined that adequate safety, tolerability, and pharmacokinetics from the previous cohort(s) have been demonstrated to permit proceeding to the next cohort. The Institutional Review Board (IRB) should be immediately notified of the dose escalation or any revised approach for review and approval.

Safety will be assessed throughout the study for all subjects. Safety assessments will include physical and detailed neurological examinations, vital signs (blood pressure, pulse rate, respiration rate, temperature and pulse oximetry), electrocardiograms (ECGs), cardiac monitoring, adverse events (AEs), and clinical laboratory tests (including hematology, serology, serum chemistry, coagulation, and urinalysis).

Blood and urine will be collected for clinical laboratory evaluations.

The Principal Investigator, in conjunction with the Sponsor may collect additional blood if necessary, for repeat laboratory or safety evaluations including AE follow up.

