## 5 SUBJECT SELECTION

### 5.1 Inclusion Criteria

All volunteers must satisfy the following criteria to be considered for study participation:

1. Understands study procedures and voluntarily provides written informed consent prior to the start of any study-specific procedures.
2. Is a healthy adult male or a healthy adult female of non-childbearing potential, 19 to 50 years of age (inclusive) at the time of screening.
3. Has a body mass index (BMI)  $\geq 18.5$  and  $\leq 32.0$  ( $\text{kg}/\text{m}^2$ ) and a body weight of no less than 50.0 kg at the time of screening and check-in.
4. Is medically healthy with no clinically significant screening results, as determined by the Principal Investigator (e.g., laboratory profiles are normal up to and including Grade 1 per DMID toxicity tables; Appendix 3), medical history, vital signs, ECG, or physical/neurological examination findings. Note: If exclusionary lab criteria are met, values may be confirmed by repeat evaluation.
5. Has not used tobacco- or nicotine-containing products (including smoking cessation products), for a minimum of 6 months before dosing.
6. Females of non-childbearing potential, based on having undergone one of the following sterilization procedures at least 6 months before dosing:
  - Hysteroscopic sterilization.
  - Bilateral tubal ligation or bilateral salpingectomy;
  - Hysterectomy; or

- Bilateral oophorectomy.
- Or is postmenopausal with amenorrhea for at least 1 year before the first dose with serum FSH levels consistent with postmenopausal status (i.e., greater than 40 mIU/mL) at screening.

Or, if female of childbearing potential, must agree to use an allowable form of birth control from screening until 14 days after study completion. The following are allowed birth control methods for this study:

- Vasectomized partner (at least 6 months before dosing);
- Non-surgical permanent sterilization (e.g., Essure® procedure) at least 3 months before dosing.
- Double barrier method (e.g., diaphragm with spermicide; condoms with spermicide).
- Intrauterine device (IUD).
- Abstinence (and must agree to use a double barrier method if they become sexually active during the study);
- Implanted or intrauterine hormonal contraceptives in use for at least 6 consecutive months before study dosing; and/or
- Oral, patch, or injected contraceptives, or vaginal hormonal device (i.e. NuvaRing®), in use for at least 3 consecutive months before study dosing.

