7. If a non-vasectomized male (or male vasectomized less than 120 days prior to study start) must agree to the following during study participation and for 90 days after the last administration of study drug:

- Use a condom with spermicide while engaging in sexual activity or be sexually abstinent
- Not donate sperm during this time.

*In the event the sexual partner is surgically sterile or postmenopausal, use of a condom with spermicide is not necessary. None of the birth control restrictions listed above are required for vasectomized males whose procedure was performed more than 120 days before study start.*

8. Is willing to answer inclusion and exclusion criteria questionnaire at check-in.
9. Is able to comply with the protocol and the assessments therein, including all restrictions.

10. Is willing and able to remain in the study unit for the entire duration of the assigned confinement period(s), return for outpatient visit(s), and receive a phone call for follow-up questioning about AEs.

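### Male contraception runs to 90 days after the last dose, but partner-pregnancy collection is required only to 30 days, leaving 60 of the 90 days without required collection

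*Protocol*

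**What the plan says.** Section 5.1, inclusion 7, applies to men described as follows: "If a non-vasectomized male (or male vasectomized less than 120 days prior to study start". They "must agree to the following during study participation and for 90 days after the last administration of study drug": use a condom with spermicide or abstain, and not donate sperm. Two carve-outs follow. Men vasectomized more than 120 days before study start are exempt, and for the condom the protocol adds: "In the event the sexual partner is surgically sterile or postmenopausal, use of a condom with spermicide is not necessary".

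Section 7.9 has two sentences with a time limit. The general one reads: "Pregnancy forms will be completed for all pregnancies reported during the study or in the 30 days after completion of the IMP". The second concerns men's partners. If the investigator learns that the "female partner of a male subject becomes pregnant during the study or in the 30 days after the completion of IMP", the partner's consent is sought to collect her pregnancy history and information on the pregnancy and birth.

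For women of childbearing potential, inclusion 6 says that they "must agree to use an allowable form of birth control from screening until 14 days after study completion".

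**The concern.** The protocol asks men to take precautions for three times as long as it asks the site to follow up a failure of those precautions. If a partner conceives between day 31 and day 90 after the last dose, section 7.9 as written requires neither a consent request nor a pregnancy form. The birth outcome would then reach the sponsor only if someone chose to report it.

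The only earlier human study described in section 1.5 gave single doses, so this is the first multiple-dose exposure. Information on a pregnancy from that period would be scarce. What is at stake is completeness of reproductive safety data. No estimate, escalation decision or stopping rule depends on it.

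**Working it through.** The plan gives no figure of its own to reproduce. The check is day arithmetic.

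**Inputs**
- Male precaution period: participation plus 90 days after the last dose (section 5.1, inclusion 7).
- Partner-pregnancy window: during the study, or 30 days after completing IMP (section 7.9).
- Last dose: Day 17 in Cohorts 1 and 2, where multiple dosing is given "after a high-calorie, high-fat meal from Day 4 through Day 17 (total of 14 days" (Synopsis, study design overview); Day 14 in Cohort 3.
- Last contact: Day 33 (+1) in Cohorts 1 and 2, Day 30 (+1) in Cohort 3 (section 6.4).
- Allocation: 9 active and 3 placebo in each of 3 cohorts (section 3).

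**Step 1. Does the wording about the study period extend the 30 days?**
Days from last dose to last contact = contact day − last-dose day.
- Cohorts 1 and 2: 33 − 17 = 16, or 34 − 17 = 17.
- Cohort 3: 30 − 14 = 16, or 31 − 14 = 17.

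Both are below 30, so the 30-day limit governs in every cohort.

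**Step 2. Size of the gap**
- Uncovered days = 90 − 30 = 60.
- Share of the post-dose period = 60/90 = 66.7%.

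**Step 3. Sensitivity to the base and to the reading of the study period**
- Adding the days from Day 1 to the last dose, when pregnancies are collected: 60/(17 + 90) = 60/107 = 56% in Cohorts 1 and 2; 60/(14 + 90) = 60/104 = 58% in Cohort 3.
- Reading the study period as the Synopsis maximum of 12 weeks, counted from Day −28: −28 + 84 = Day 56, which is 39 days (Cohorts 1 and 2) or 42 days (Cohort 3) after the last dose. The gap is then 51/90 = 57% or 48/90 = 53%. This reading is strained, because each subject's schedule ends with the call, but even so more than half of the period stays uncovered.

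**Step 4. Does another section close the gap?**
Section 7.6 takes new related SAEs up to 30 days after last contact: 33 + 30 − 17 = 46 days after the last dose in Cohorts 1 and 2, and 30 + 30 − 14 = 46 in Cohort 3 (47 if the call is a day late). It covers SAEs, not pregnancies. A congenital anomaly is an SAE under section 7.1.2, but a birth following conception on days 31 to 90 would come long after that window. Section 7.9 is therefore the only route.

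**Step 5. How many subjects**
Men on active drug: at most 3 × 9 = 27. Placebo men (3 × 3 = 9) are under the same rule but carry no exposure. The 27 falls with each woman enrolled, each man vasectomized more than 120 days earlier, and each man whose partner is sterile or postmenopausal.

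**The case against.** The strongest reply is that these are two rules with different purposes: one a precaution for participants, the other a data-collection rule. Neither refers to the other, a site can follow both to the letter, and nothing in the protocol says that they must have the same length. That is right as far as it goes. The finding is a mismatch to reconcile, not a logical contradiction. It still leaves a period in which the protocol demands precaution and asks for no data if precaution fails, and it gives no reason for the difference.

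Four stronger readings are tempting and are not supported.

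- *That pregnancies after day 30 are barred from reporting.* Section 7.9 does not forbid a later report. Collection there is already passive, since it starts when the investigator happens to learn of a pregnancy. The gap is in what is required.
- *That the number was copied from the female rule, where contraception and reporting both end 30 days after the last dose.* This holds only if study completion in inclusion 6 means the follow-up call: 33 + 14 = Day 47 = 17 + 30, and 30 + 14 = Day 44 = 14 + 30. The term is undefined. Section 6.8 and Tables 6 and 7 attach the end of study to Day 26 or Day 23. Then 26 + 14 = Day 40 and 23 + 14 = Day 37, each 23 days after the last dose. The origin of the 30 days cannot be established from the document.
- *That a drug-related risk on days 31 to 90 is shown.* Inclusion 7 gives no reason for 90 days, and the pharmacokinetic follow-up ends at 72 hours. The 90 days show only where the protocol wants precaution.
- *That all 36 subjects are affected.* That count includes 9 on placebo and ignores women and exempt men.

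It is also fair to say that 67% is a share of calendar days. The document gives no basis for an expected number of pregnancies, which in a study of this size and with contraception required is likely to be very small.

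**Conclusion.** The point holds in limited form. For men covered by inclusion 7, required collection of partner pregnancies stops 60 days before the precaution period does: 60 of 90 post-dose days (67%), or 56% to 58% if the dosing days are counted in the base. It concerns at most 27 actively treated subjects, and realistically fewer. The result assumes the three planned cohorts with no additional ones, dosing completed on schedule, and a study period that ends for each subject at the follow-up call. It does not depend on how the female windows compare. It affects completeness of safety data and no statistical result. It is worth correcting because the correction is cheap, not because many events are likely to be missed.

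**What to change.** Reconcile inclusion 7 and section 7.9 on the data-collection side, so that the partner-pregnancy window in 7.9 covers the period set in inclusion 7. Edit two sentences, the one on partner consent and the one on pregnancy forms. Changing only the first would leave consent sought over the longer period while forms were required only to 30 days. Add a matching line to the consent document, and remind male subjects at the existing Day 30 or Day 33 call to report a partner pregnancy within that period. If the sponsor intends the shorter window, 7.9 should say so and give the reason.

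The cost is two edited sentences, a consent change that needs IRB review, and a reporting route kept open 60 days longer. No visit or procedure is added, and no contraception, eligibility or dosing rule is altered. Separately, defining study completion in inclusion 6 would settle when the female period ends.
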